14.3.1.1 Subgroup Analysis

SRI-6 response among serologically active subjects

Analysis of SRI-6 response among serologically active subjects will be repeated for subgroup A from Table 4 (HDA vs non-HDA). The estimated OR, together with associated two-sided 95% CI of the estimated OR, nominal p-values from the logistic regression model, comparing each evobrutinib treatment group to placebo will be presented. No multiple testing adjustments will be performed.

14.3.2 Time to first flare, flare-free status and AFR

Time to first flare, flare-free status, and annualized flare rate, during the 52-week treatment period, will be analyzed separately, each assessed with flare defined as:

- Severe BILAG A flare (Key secondary endpoint, see Section 14.2.2.2)
- Moderate to Severe (BILAG A or 2B) flare
- Severe SFI flare

14.3.2.1 Definitions

BILAG flare severity is defined as follows:

- Severe flare: ≥ 1 BILAG A score in any organ system due to items that are new or worse, compared to the BILAG evaluation at the previous visit
- Moderate flare: at least 2 BILAG B scores in any organ systems due to items that were new or worse, and without meeting the criteria for the severe flare, compared to the BILAG evaluation at the previous visit and no BILAG A meeting the condition of severe flare
- Mild flare: 1 single BILAG B score in any organ systems due to items that were new or worse, or at least 3 BILAG C scores in any organ systems due to items that were new or worse, compared to the BILAG evaluation at the previous visit and no BILAG A and no more than one BILAG B meeting the condition of severe or moderate flare
- No flare: defined as not meeting any of the above criteria.

‘Due to items that were new or worse’ means that if the assigned Grade A/B or C contains ANY ITEM which is WORSE or NEW, such grade will be included into the flare consideration. This is valid for clinical organ domains. For laboratory organ domains (i.e. renal and hematological) where items are not worse/new, there must be an increase in score from B to A or C to B for flare to be considered.

For BILAG flares, the time to first flare is defined as follows:

Time to first flare (days) = Date of visit where the first flare has been diagnosed – Date of randomization + 1
For SFI severe flares, the time to first severe flare is defined as follows:

$$\begin{aligned} & \text{Time to first severe flare (days)} \\ &= \text{Date of first flare since last flare assessment from the SFI2 form of the eCRF} \\ & - \text{Date of randomization} + 1 \end{aligned}$$

A subject has a flare-free status at Week 52 if no flares have been reported during the 52-week treatment period. Subjects who discontinue study prior to Week 52, without having a flare are counted as not being flare-free at Week 52.

The unadjusted AFR is the total number of flares from all subjects in the analysis set, divided by the total exposure time from all subjects in the analysis set. At the subject level, the unadjusted AFR is the total number of flares experienced by the subject divided by the total exposure time of this subject.

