14.3.2.2 Statistical analysis

Table 20, Table 21 and Table 22 provide details of the Flare endpoints.

Table 20 : Time to first flare

Endpoint	Analysis method	Data Handling Notes

 Time to first severe BILAG A flare (a) Time to BILAG A or 2B Moderate to Severe flare (b) Time to first severe SFI flare (c) 	As described in Section 14.2.2.1 (no sensitivity/supportive analyses will be performed)	See Section 14.2.1 for censoring rules

(a) A Severe (BILAG A) flare is defined as at least one BILAG A score in any organ system due to items that are new or worse, compared to the BILAG evaluation at the previous visit, during the 52-week treatment period. Time to first severe BILAG A flare analysis is described in Section 14.2.2.1 as part of key secondary endpoint.
 
(b) A Moderate to Severe (BILAG A or 2B) flare is defined as at least one BILAG A grade or two BILAG B grade in any organ system due to items that are new or worse, compared to the BILAG evaluation at the previous visit.
 
(c) The severity of SFI flare is recorded in the eCRF (Mild/Moderate versus Severe). However, for statistical analysis purpose, the severity will be re-derived using the SLEDAI total score as well as each sign or symptom recorded in the SFI1, SFI2, SFI3 forms of the eCRF (see Appendix 18.1.4 for a definition of Mild/Moderate or Severe flare). As the onset of new flare date or stabilization/resolution date is not recorded in the eCRF, if an investigator records a flare in two consecutive visits, it will be assumed that the flares are distinct events (i.e., when a new SFI flare is recorded in the eCRF, it will be assumed the previous one is stabilized/resolved). Therefore, only unique records from the SFI forms of the eCRF will be counted, assuming that distinct records represent distinct flare events.
		

Table 21 : Flare free status during the 52-week Treatment Period

Endpoint	Analysis method	Data Handling Notes

 BILAG 2004 Flare-free status (a) SFI flare-free status (b) 	
 Logistic regression Descriptive statistics 	Subjects who discontinue study prior to Week 52, without having a flare are counted as not being flare-free

(a) BILAG 2004 flare-free is defined as having only BILAG scores equal to D or E during the 52-week treatment period.
 
(b) SFI flare-free is defined as having no SFI flare during the 52-week treatment period.
		

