18.1.3 SLEDAI-2K

The Total score of the SLEDAI-2K is calculated as the sum of the weights of the descriptors marked as present by the investigator. The weights corresponding to each of the 24 descriptors are described in the table below:

Table 33: SLEDAI scoring

Descriptor	Weight
Seizure	8
Psychosis	8
Organic brain syndrome	8
Visual disturbance	8
Cranial nerve disorder	8
Lupus headache	8
Cerebrovascular accident	8
Vasculitis	8
Arthritis	4
Myositis	4
Urinary casts [#]	4
Hematuria [#]	4
Proteinuria [#]	4
Pyuria [#]	4
Rash	2
Alopecia	2
Mucosal ulcers	2
Pleurisy	2
Pericarditis	2
Low complement* [#]	2
Increased DNA binding* [#]	2
Fever	1
Thrombocytopenia [#]	1
Leukopenia [#]	1

*blinded descriptor

[#]laboratory components

Handling with blinded descriptor: As “Increased DNA binding” and “Low complement” are blinded items, the SLEDAI-2K total score will have to be derived for primary analysis with the laboratory unblinded values. “Increased DNA binding” item is defined as “>25% binding by Farr assay or above normal range for testing laboratory”. The parameter to take into account in laboratory data is “anti-Double Stranded DNA”. Increased DNA binding will be derived as ‘present’ if the anti-dsDNA value is positive (i.e. > 15 U/mL). “Low complement” item is defined as “decrease in C3 or C4 below the lower limit of normal for testing laboratory”. The parameters to take into account in laboratory data are “Complement C3” and “Complement C4”.

Total score used for statistical analysis will be re-calculated for all timepoints except screening and Day 1 with the unblinded values of Increased DNA binding and Low complement. The total score for the next visits as stated by the investigator in the eCRF will not be used in any statistical analysis.

Handling of missing items in SLEDAI-2K scores and change from baseline scores:

Actual scores

If the missing clinical component has weight > 4 in the overall score (see [Table 33](#)), then no imputation is performed. The SLEDAI-2K score will be missing.

If the missing clinical component has weight ≤ 4 in the overall score (see [Table 33](#)) or laboratory components missing, then the missing values will be imputed with the value of previous analysis visit. Only value assessed post-Day 1 dose (i.e. after baseline) can be used for imputation. If at least one item is still missing, then SLEDAI-2K score will be calculated based on available data.

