18.1.4 SLEDAI Flare Index

The SFI can be used with any version of the SLEDAI and will be used with the SLEDAI-2K for the purposes of this trial.

A mild/moderate flare is defined as any of the following

- Increase in SLEDAI-2K total score of 3 points or more (but total score not to more than 12).
- New or worse discoid, photosensitive, profundus, cutaneous vasculitis, bullous lupus; or nasopharyngeal ulcers; or pleuritic; or pericarditis; or arthritis; or fever due to SLE.
- Increase in prednisone, but not to > 0.5 mg/kg/day.
- Added NSAID or hydroxychloroquine (or chloroquine) for SLE activity.
- ≥ 1.0 increase in PGA score, but score not to exceed 2.5 (assuming the PGA score has been transformed to a 0-3-point scale).

A severe flare is defined as any of the following:

- Increase in SLEDAI-2K total score leading to total score > 12.
- New or worse central nervous system SLE; or vasculitis; or nephritis; or myositis; or platelets < 60,000/mm³, or hemolytic anemia with hemoglobin < 70 g/L or decrease in hemoglobin > 30 g/L AND requiring: double prednisone, or prednisone increase to > 0.5 mg/kg/day, or hospitalization due to SLE.
- Increase in prednisone to > 0.5 mg/kg/day.
- New cyclophosphamide, azathioprine, methotrexate, or mycophenolate for SLE activity.
- Hospitalization for SLE activity.
- Increase in PGA score leading to total score > 2.5 (assuming the PGA score has been transformed to a 0-3-point scale).

SFI used for statistical analysis will be re-calculated with the SLEDAI-2K total score derived with the unblinded value of Increased DNA binding and Low complement.

Subjects with missing SFI assessment for a visit will be counted as missing in the SFI summary statistic table for that visit.

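### Time to first severe SFI flare relies on an eCRF flare date that the SAP elsewhere says is not recorded, and some re-derived severe flares can have no such date, with no fallback

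*SAP*

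**What the plan says.** Section 14.3.2.1 gives two event-time formulas. BILAG flares are dated by the visit at which the first flare was diagnosed. Severe SFI flares are dated by "Date of first flare since last flare assessment from the SFI2 form of the eCRF", minus the randomization date, plus one.

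Note (c) to Table 20 (Section 14.3.2.2), attached to this same endpoint and repeated under Table 22, justifies counting flares at consecutive visits as separate events with the words "As the onset of new flare date or stabilization/resolution date is not recorded in the eCRF". The note also sets aside the investigator's severity grade for analysis: "the severity will be re-derived using the SLEDAI total score as well as each sign or symptom recorded in the SFI1, SFI2, SFI3 forms".

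Appendix 18.1.4 goes further: "SFI used for statistical analysis will be re-calculated with the SLEDAI-2K total score derived with the unblinded value of Increased DNA binding and Low complement". One criterion that suffices alone for a severe flare is "Increase in SLEDAI-2K total score leading to total score > 12".

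Appendix 18.1.3 says that the two serology items "are blinded items, the SLEDAI-2K total score will have to be derived for primary analysis with the laboratory unblinded values". It adds: "The total score for the next visits as stated by the investigator in the eCRF will not be used in any statistical analysis".

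For censoring, Table 20 refers to Section 14.2.1. Those rules cover only subjects without a flare.

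**The concern.** A time-to-event endpoint needs a date for every event. Here the date comes from the investigator's form, while the event itself is decided by a program using laboratory values that the investigator did not see. The two sources need not agree. The SAP also appears to deny that the date exists.

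If the rule is programmed as written, a severe flare without an SFI2 date must be dropped, censored or dated by a choice that was not pre-specified. A severe flare that does have a date may receive that of a milder flare, because the formula does not restrict the date to severe flares.

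**Working it through.** The plan states no figure to reproduce. The check sets the definitions side by side and does hand arithmetic on the SLEDAI-2K weights.

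**1. Is the date available?** A date of the first flare since the last assessment is, in ordinary language, the onset date of a new flare. Section 14.3.2.1 names a form that holds it. Note (c) says such a date is not recorded. The two could be reconciled if SFI2 holds one first-flare date per interval and no onset and resolution dates for each flare, but the SAP does not say so.

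**2. Does the date belong to the severe flare?** The formula asks for the first flare since the last assessment, of any severity. If a mild or moderate flare and then a severe one fall in the same interval, the severe event takes the earlier date. The formula also names SFI2 only, while severity uses SFI1, SFI2 and SFI3.

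**3. Can a re-derived severe flare lack the date?** Inputs from Table 33: low complement and increased DNA binding weigh 2 each. Two assumptions are mine: the investigator's total after Day 1 omits the blinded items, and an increase is judged against the previous assessment.

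Let x be the investigator's total and k the number of serology items present (0, 1 or 2). The re-calculated total is x + 2k, and the score criterion needs x + 2k > 12.

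- k = 1: x > 10, so recorded totals of 11 or 12 cross the threshold.
- k = 2: x > 8, so recorded totals of 9 to 12 cross it.

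The re-calculated score must also rise: (change in x) + 2 × (change in k) > 0. A recorded rise of 3 points or more, to a total not above 12, is already a mild/moderate flare under 18.1.4. The investigator could have recorded and dated that one. The undated cases therefore have a change in x of at most 2 and no other SFI criterion met. Two examples:

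| | Previous visit | Current visit | Investigator's score | Re-calculated |
|---|---|---|---|---|
| Serology unchanged (k = 1) | x = 10, total 12 | x = 12, total 14 | rise of 2, no flare by score | rise to > 12, severe |
| Serology newly positive (k from 0 to 2) | x = 10, total 10 | x = 10, total 14 | no change | rise to > 12, severe |

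In both rows the program derives a severe flare at a visit where the investigator had no score-based reason to enter one.

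**4. Is there a fallback?** None is given in Sections 14.3.2.1, 14.3.2.2, 14.2.1 or Appendix 18.1.4.

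**5. How far apart are the candidate dates?** Table 51 places visits in the 52-week period 28 days apart (for example Day 57 − Day 29 = 28). An onset date and the visit date can therefore differ by up to about four weeks. In the extension the Table 51 target days are 1, 169, 365 and 745. If assessments follow them, the gaps are 168, 196 and 380 days.

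**The case against.** The eCRF is not shown. Section 14.3.2.1 names a particular field on a particular form, which is good evidence that the field exists. Note (c) addresses another question, namely whether consecutive flares are one event or two. A reader might infer that the SFI2 date was never collected. The documents do not establish that. They establish only that the two statements conflict as worded.

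Note (c) also speaks of re-deriving severity and of counting unique records on the SFI forms. On that reading the events are the flares that investigators recorded, and an upgraded mild/moderate flare keeps its date. This stands for upgraded flares. It does not close the gap, because 18.1.4 re-calculates the SFI itself, and the SAP does not say that a re-calculated flare without an investigator's record is to be ignored.

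A reader might also infer that every flare crossing 12 through serology is affected. That is too strong: an increase is required, serology positive at both visits adds equally to both scores, and many such visits will meet another recorded criterion.

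Finally, a date rule different from BILAG's is defensible. SFI criteria include hospitalization and treatment changes, which happen between visits. Discarding valid SFI2 dates for all flares would lose information, particularly with the wide extension windows. This stands and limits the remedy.

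**Conclusion.** The point holds in a limited form. The SAP contradicts itself on whether a flare onset date is recorded, does not tie the date to the severe flare, and leaves the event time undefined for a severe flare produced only by the re-calculation. The last part rests on the two assumptions stated with the arithmetic.

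The number of affected flares cannot be derived from the document, and nothing in it shows a bias between arms, so neither should be inferred. The reach is small. Time to first severe SFI flare is an other secondary endpoint with nominal two-sided p-values (Section 14.3), outside the hierarchical procedure of Section 14.1.2.4. Annualized flare rate and flare-free status do not use this event-time formula. The extension counterpart (Section 14.6, Table 25) is descriptive. It is censored at 23 March 2020, so the dating rule could decide whether a flare close to that day is counted. The point should be corrected but does not threaten the trial's main conclusions.

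**What to change.** 1. Reconcile Section 14.3.2.1 with note (c) of Tables 20 and 22 by stating exactly which flare dates the SFI2 form holds.
2. Define the event as the first visit at which the re-derived SFI meets the severe definition, and say whether a flare without an investigator's record counts.
3. Use the visit date for every re-derived severe flare with no SFI2 date for that interval. If the SFI2 date is in fact not collected, use the visit date for all SFI flares.
4. Where an SFI2 date is kept, require that it belong to the severe flare and fall within that interval.

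No new data are needed. The cost is SAP wording and a small change to the derivation program. Version 4.0 was written after the primary analysis results had been reviewed, so the report should say which rule the primary analysis used and present any changed dating as a later clarification.

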14.3.2.2 Statistical analysis

Table 20, Table 21 and Table 22 provide details of the Flare endpoints.

Table 20 : Time to first flare

Endpoint	Analysis method	Data Handling Notes

 Time to first severe BILAG A flare (a) Time to BILAG A or 2B Moderate to Severe flare (b) Time to first severe SFI flare (c) 	As described in Section 14.2.2.1 (no sensitivity/supportive analyses will be performed)	See Section 14.2.1 for censoring rules

(a) A Severe (BILAG A) flare is defined as at least one BILAG A score in any organ system due to items that are new or worse, compared to the BILAG evaluation at the previous visit, during the 52-week treatment period. Time to first severe BILAG A flare analysis is described in Section 14.2.2.1 as part of key secondary endpoint.
 
(b) A Moderate to Severe (BILAG A or 2B) flare is defined as at least one BILAG A grade or two BILAG B grade in any organ system due to items that are new or worse, compared to the BILAG evaluation at the previous visit.
 
(c) The severity of SFI flare is recorded in the eCRF (Mild/Moderate versus Severe). However, for statistical analysis purpose, the severity will be re-derived using the SLEDAI total score as well as each sign or symptom recorded in the SFI1, SFI2, SFI3 forms of the eCRF (see Appendix 18.1.4 for a definition of Mild/Moderate or Severe flare). As the onset of new flare date or stabilization/resolution date is not recorded in the eCRF, if an investigator records a flare in two consecutive visits, it will be assumed that the flares are distinct events (i.e., when a new SFI flare is recorded in the eCRF, it will be assumed the previous one is stabilized/resolved). Therefore, only unique records from the SFI forms of the eCRF will be counted, assuming that distinct records represent distinct flare events.
		

Table 21 : Flare free status during the 52-week Treatment Period

Endpoint	Analysis method	Data Handling Notes

 BILAG 2004 Flare-free status (a) SFI flare-free status (b) 	
 Logistic regression Descriptive statistics 	Subjects who discontinue study prior to Week 52, without having a flare are counted as not being flare-free

(a) BILAG 2004 flare-free is defined as having only BILAG scores equal to D or E during the 52-week treatment period.
 
(b) SFI flare-free is defined as having no SFI flare during the 52-week treatment period.
		

Logistic regression model:

For each definition of flare-free, the comparison of each evobrutinib group to the placebo group using proportion flare-free during the 52-week treatment period, will be based on a logistic model for the odds of flare-free status, with treatment group and stratifications of randomization as factors.

For each treatment comparison (evobrutinib versus placebo), the adjusted OR with 95% CI, and p-value will be reported.

An example of SAS code is available in Appendix 18.9.

Descriptive statistics:

The proportion of subjects having a BILAG flare will be presented by visit, severity and treatment group.

For each definition of flare, descriptive statistics (number and percentage of subjects) for flare-free status will be provided by treatment group. In particular, the number (proportion) of subjects with ≥ 1 flare, number (proportion) of subjects with 0 flares, number (proportion) of subjects discontinuing treatment prior to Week 52 among subjects with 0 flares will be reported.

Table 22 : AFR

Endpoint	Analysis method	Data Handling Notes

 • Severe BILAG A AFR (a) • Moderate to severe (BILAG A or 2B) AFR (b) • Severe SFI AFR (c) 	
 • Negative binomial (NB) model, with offset equal to log of exposure time, • Descriptive statistics 	As observed

(a) A severe (BILAG A) flare is defined as at least one BILAG A score in any organ system due to items that are new or worse, compared to the BILAG evaluation at the previous visit, during the 52-week treatment period.
 
(b) A Moderate to Severe (BILAG A or 2B) flare is defined as at least one BILAG A grade or two BILAG B grade in any organ system due to items that are new or worse, compared to the BILAG evaluation at the previous visit.
 
(c) The severity of flare is recorded in the eCRF (Mild/Moderate versus Severe). However, for statistical analysis purpose, the severity will be re-derived using the SLEDAI total score as well as each sign or symptom recorded in the SFI1, SFI2, SFI3 forms of the eCRF (see Appendix 18.1.4 for a definition of Mild/Moderate or Severe flare). As the onset of new flare date or stabilization/resolution date is not recorded in the eCRF, if an investigator records a flare in two consecutive visits, it will be assumed that the flares are distinct events (i.e., when a new SFI flare is recorded in the eCRF, it will be assumed the previous one is stabilized/resolved). Therefore, only unique records from the SFI forms of the eCRF will be counted, assuming that distinct records represent distinct flare events.
		

NB model:

The comparison of each evobrutinib treatment group to the placebo group using AFR at Week 52 will be based on a NB model for flare count, with offset equal to the log of exposure time. Subjects who prematurely discontinue from treatment will be analyzed according to the number of days on treatment and number of flares observed at the time of treatment discontinuation. Missing post-baseline flare assessment will be counted as no flare in AFR analysis.

The AFR analysis will be performed on the mITT analysis set using the NB model, with treatment group as main effect and randomization strata as covariates. The adjusted AFR ratio

for treatment comparison versus placebo, the 95% CI of the AFR ratio and the 2-sided nominal p-value from the NB model will be presented.

The NB model will be computed with the SAS GENMOD procedure. If the model does not converge, appropriate method will be applied to resolve the issue (e.g. removal of covariate). An example of SAS code is available in Appendix 18.9.

Descriptive statistics:

Summary statistics (mean, SD, median, Q1, Q3, min, and max) will be presented by treatment group for:

- Number of flares,
- Time on treatment (subject-years),
- Total number of flares per subject-year.

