- The protocol specifies that flare-free status will be analyzed separately depending on severity, but in this IAP flare-free status is defined as not having any flares (defined with BILAG 2004 and SFI, separately) during the 52-week treatment period.
- The protocol mentions several endpoints for the analysis of corticosteroid usage over time. The first endpoint (i.e., reduction from baseline in prednisone-equivalent CS dose by $\geq 25\%$ to a dose of ≤ 7.5 mg/day, with no BILAG A or 2B flare in disease activity at that visit) is removed from this IAP. Analysis of the clinically meaningful reduction in CS dose from Baseline (defined as a reduction of daily prednisone-equivalent CS dose $\geq 25\%$ to a dose of ≤ 7.5 mg/day by Week 40 and sustained through Week 52 AND no new BILAG A organ domain scores and no more than one new BILAG B organ domain score during Weeks 40 through 52) will be sufficient.
- SRI definition specified in the protocol includes ‘no discontinuation of investigational product’, but this condition has been removed from this IAP (see Section 14.1.1). Subjects with missing response at Week 52 have been added as a condition of non-SRI responder, meaning that all subjects who prematurely discontinued treatment will be considered as non-SRI responder.
- For definition of SRI responses, LDA Definition #2, LLDAS and BICLA, EAC-treatment failure assessment will be used to consider subjects as non-responder in these 3 endpoints.
- Due to study termination, the analysis of Japanese cohort and LTE analysis will be performed simultaneously. The Japanese cohort will not be explored for consistency, the listings produced for the PA will be rerun including all Japanese subjects. A safety summary of Asia-Pacific subjects will be presented during the 52-Week treatment period (see Section 14.1.4). The LTE analysis will be reduced with a focus on safety, further details can be found in Sections 14.6 and 15.

8 Protocol Deviations and Analysis Sets

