18.1 Definitions of Efficacy Endpoints

18.1.1 BILAG 2004 Disease Activity Index

The BILAG 2004 Disease Activity Index (Yee 2009, Yee 2010) evaluates SLE activity in a number of organ systems, based on the principle of “physician’s intention to treat” (refer to Manual of Procedures). The primary purpose of the BILAG in this study is to assess possible worsening in specific organ systems. Additional analyses of improvements in disease activity as assessed by the BILAG 2004 will also be done.

A separate alphabetic score is assigned to each organ system, corresponding in general to the following definitions:

- BILAG A: Severe disease activity requiring any of the following treatments (e.g., systemic high dose oral CS, intravenous pulse CS, systemic immunosuppressants, or therapeutic high dose anticoagulation in the presence of high dose CS or ≥ 20 mg prednisone). Note that in the context of a CTP with medication restrictions and blinded IMP, the term “requiring” is not taken literally, but indicates that if all else were equal this would be the degree of treatment indicated. It is also understood that some subjects respond to different levels of medication than others, so that in assessing subjects with the BILAG “intent to treat” really means that most subjects with this degree of symptom would require this level of treatment, not necessarily the subject in question.
- BILAG B: Moderate disease activity requiring treatment with systemic low dose oral glucocorticoids, intramuscular or intra-articular or soft tissue CS injection, topical CS or immunosuppressants, or symptomatic therapy such as antimalarials or NSAIDs.
- BILAG C: Mild disease
- BILAG D: System previously affected but now inactive
- BILAG E: System never involved

The BILAG 2004 is evaluated by scoring each of a list of signs and symptom as: improving (1); same (2); worse (3); new (4); not present (0); not done (ND). For some items, appropriate responses may be: Y/N or numerical values where indicated, or Y/N confirm this is due to SLE activity.

All signs and symptoms scored must be due to SLE. Use of a glossary provided with the BILAG 2004 instrument and training of assessors in use of the instrument are essential to obtaining reliable and consistent results.

Use of the BILAG 2004 index for evaluating flares has been identified as a robust way of evaluating the efficacy of drugs; this judgment has been corroborated by external advisors and regulatory authorities.

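### Table 21 note (a) defines BILAG flare-free as a full year of D or E grades, which is an inactivity criterion and conflicts with the no-flare definition in SAP Sections 7 and 14.3.2.1

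*SAP*

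**What the plan says.** Three places in the SAP define BILAG flare-free status, and they do not agree.

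- **Section 7**, which lists changes from the protocol: "in this IAP flare-free status is defined as not having any flares (defined with BILAG 2004 and SFI, separately) during the 52-week treatment period".
- **Section 14.3.2.1**: "A subject has a flare-free status at Week 52 if no flares have been reported during the 52-week treatment period". The same section sets the flare tiers. Severe is "≥ 1 BILAG A score in any organ system due to items that are new or worse, compared to the BILAG evaluation at the previous" assessment. Moderate needs at least two such B grades. Mild needs one such B grade, "or at least 3 BILAG C scores in any organ systems due to items that were new or worse". The remaining category is "No flare: defined as not meeting any of the above criteria". In the renal and haematological domains, where items are not rated new or worse, the grade must rise from B to A or from C to B.
- **Section 14.3.2.2, Table 21 note (a)**: "BILAG 2004 flare-free is defined as having only BILAG scores equal to D or E during the 52-week treatment period".

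Note (b) to the same table defines SFI flare-free as having no SFI flare. Section 14.3.2.2 then plans a logistic regression of flare-free status, adjusted for the randomization strata. It also plans counts of subjects with at least one flare, with zero flares, and of those stopping treatment before Week 52 among subjects with zero flares.

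**The concern.** A flare is a change from the previous visit, whereas a BILAG grade is a level of activity. Section 18.1.1 glosses grade C as "BILAG C: Mild disease", D as an organ system now inactive, and E as one never involved. Requiring only D or E for a year therefore asks for sustained inactivity in every domain and does not measure absence of flares.

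A programmer cannot satisfy both rules, and the SAP does not say which one governs. If note (a) is followed, the adjusted odds ratio labelled flare-free describes a different and stricter endpoint. It would also sit beside descriptive counts built on the no-flare meaning. The LTE analysis is exposed as well, because Table 25 in Section 14.6 analyses flare-free status as in Section 14.3.2.

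**Working it through.** The plan states no rate, sample size or power for flare-free status, so there is no figure to reproduce. The check compares the two rules directly.

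**1. One subject under both rules.** Under Section 18.1.1.4, severe arthritis recorded as same gives grade A, and recorded as improving gives grade B. Moderate arthritis recorded as improving gives grade C. A completer who moves A, B, C in this way, with no item new or worse and all other domains inactive, never meets a flare tier. By Section 14.3.2.1 the subject is flare-free; by note (a) the subject is not. The same holds for a subject with one unchanging C grade.

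**2. All per-visit patterns.** Take nine organ domains (Sections 18.1.1.1 to 18.1.1.9). Count how many carry a stable A, B or C and how many carry an A, B or C due to new or worse items; the rest are D or E.

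- Total count patterns: C(15,6) = 5005.
- No flare under Section 14.3.2.1 means no new or worse A or B, and at most two new or worse C. With 0, 1 or 2 such C grades, the stable grades can fill at most 9, 8 or 7 domains: C(12,3) + C(11,3) + C(10,3) = 220 + 165 + 120 = 505.
- Satisfying note (a): 1 pattern (all D or E).
- No flare but failing note (a): 505 − 1 = 504.
- Satisfying note (a) while having a flare: 0.

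Note (a) therefore selects a strict subset of the no-flare state. These are counts of patterns and not proportions of patients.

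**3. Activity at Screening.** The sample-size text (Section 8.2.1) refers to subjects with SLEDAI-2K of at least 6. In Table 33 the two serological descriptors weigh 2 each, so serology gives at most 2 + 2 = 4 points. At least 6 − 4 = 2 points must come from clinical, urinary or haematological descriptors. Subjects thus start with some non-serological activity.

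**4. How many could qualify.** Table 51 has 13 post-baseline visits, Weeks 4 to 52. Let q be the chance that all nine domains are D or E at one visit. The document gives no q, so these values are assumptions:

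| Assumed q | Independent visits, q^13 | Perfectly correlated visits, q |
|---|---|---|
| 0.5 | 0.00012 | 0.5 |
| 0.7 | 0.0097 | 0.7 |
| 0.9 | 0.254 | 0.9 |

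Visits within a subject are correlated, so the independence column is too low. The range is too wide to support any specific proportion.

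**5. Consistency within Section 14.3.2.2.** Under the no-flare rule, flare-free subjects are those with zero flares who did not discontinue early. Under note (a) that relation fails, because completers with zero flares can be counted as not flare-free.

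**The case against.** The best defence is that note (a) is loose wording in a table footnote. Section 14.3.2.1 is the section headed as definitions, Section 7 records the intent, and nothing says Table 21 prevails. The no-flare proportion would also be reported by arm through the zero-flare counts, whichever rule drove the model. These points stand. They limit the damage to one adjusted odds ratio and its reporting, but they do not remove the conflict. Note (b), the rule for discontinuers in Table 21 and the descriptive counts all use the no-flare meaning, so note (a) is the outlier.

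Stronger conclusions are tempting, but the document does not support them:

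- **That almost nobody would qualify, or that the logistic model could not be fitted.** A reader might infer this from the 13 visits and the activity at Screening. No BILAG grade distribution is given, and the result depends wholly on assumed values.
- **That one low lymphocyte or white cell count always disqualifies a subject.** Section 18.1.1.9 does not score haematological items recorded as not SLE related.
- **That the result would contradict time to first flare or the annualized flare rate.** A strict subset of no-flare differs from those results without contradicting them. Tables 20 and 22 use severe or moderate-to-severe flares, so they would differ from an any-flare status even after correction.
- **That a confirmatory claim is at risk.** Section 14.3 makes these p-values nominal, and the hierarchy in Section 14.1.2.4 covers only the two primary and two key secondary endpoints.

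**Conclusion.** Note (a) is wrong as written. It conflicts with Sections 7 and 14.3.2.1 and with the rest of Table 21, and it classifies completers with stable or improving A, B or C grades as not flare-free although they had no flare. This follows from the text alone and rests on no assumed rate. Section 7 states the no-flare meaning as the deliberate choice, so note (a) cannot be read as an intended departure.

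The numerical effect cannot be computed from the document. That only a small fraction would meet note (a) is a reasonable inference from the activity at Screening and the grading rules, but it remains an inference. The consequence is confined to an other secondary endpoint with nominal p-values and to its descriptive LTE counterpart. The correction is worth making, but the primary and key secondary conclusions do not depend on it.

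**What to change.** Replace note (a) with: *no BILAG flare as defined in Section 14.3.2.1 during the 52-week treatment period*. This mirrors note (b). Keep the existing rule that subjects who discontinue early without a flare are not flare-free. Avoid the term on-treatment in the new wording, because Section 9.7 extends it to End of Study. If the all-D/E state is of interest, name it *BILAG inactive* and report it separately.

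Reconcile one related point at the same time. Section 14.3.2 lists flare-free status under three severity-specific definitions (BILAG A, BILAG A or 2B, severe SFI), whereas Section 7 and Table 21 use any flare, for BILAG and SFI separately. Section 7 documents the any-flare choice, so the correction to note (a) should not silently reverse it.

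The text change is one table note, and any re-derivation uses data already collected. Version 4.0 of the plan, however, follows review of the primary analysis results (Sections 6.3 and 6.4). The study report should therefore state which rule was programmed and identify any re-derivation as made after those results.
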